12.2.1 Objective response rate

The primary endpoint, ORR, will be estimated for each cohort with 95% exact CIs. The primary analysis will be based on the programmatically derived ORR based on ICR assessments, and using all scans regardless of whether they were scheduled or not. An analysis of ORR using the results of the programmatically derived RECIST using the site investigator tumour data from all scans will be conducted as a sensitivity analysis to confirm the results of the primary analysis using data derived from the eCRFs. An additional sensitivity analysis will be performed on programmatically derived ORR using ICR data (RECIST modified for confirmation of progression) to determine if there is any difference when using progression confirmation rules. The primary analysis population for ORR will be a subset of the FAS population (ie, dosed patients with a baseline tumour assessment that indicates measurable disease per the ICR).

Summaries will be produced that present the number and percentage of patients with a tumour response (CR/PR). The number (%) of patients with a confirmed response and the number (%) of patients with a single visit response (ie, an unconfirmed response) will also be presented.

Summaries of ORR for each cohort will also be presented for the irRECIST 1.1 data obtained from the ICR.

A supportive analysis of patients with unselected PD-L1 status will be conducted consisting of a combined population of PD-L1 positive and PD-L1 negative/unknown patients, including those also enrolled after the protocol amendment to only recruit patients with PD-L1 positive status (ie, all Cohort 2 patients). This will use a weighted approach based on the observed

prevalence of PD-L1 positive, PD-L1 negative and PD-L1 unknown patients from the unselected sample pre-amendment. Further details of this approach will be provided in the SAP.

Furthermore, summaries of ORR (using the programmatically derived ORR based on ICR assessments) may also be presented by cohort for the PD-L1 negative patients in Cohort 1, and additionally, for all patients in a combined population of Cohorts 1 and 2.

12.2.2 Duration of response

Kaplan Meier plots of DoR based on the ICR assessment of RECIST will be presented for each cohort. Median DoR will also be summarised. Only patients who have a confirmed response will be included in this summary table. Duration of response will also be analysed based upon the site investigator tumour data.

The DoR will also be summarised using the irRECIST 1.1 data obtained from ICR.

Furthermore, DoR (using the programmatically derived DoR based on ICR assessments) may also be summarised by cohort for the PD-L1 negative patients in Cohort 1 and, additionally, for all patients in a combined population of Cohorts 1 and 2.

12.2.3 Disease control rate

The DCR based upon the ICR assessment of RECIST will be summarised (ie, number of patients [%] for each cohort). Disease control rate will also be summarised based upon the site investigator tumour data.

Disease control rate will also be summarised using the irRECIST 1.1 data obtained from ICR.

12.2.4 Time to response

The TTR, based upon the ICR assessment of RECIST, will be summarised (ie, number of patients [%] based upon the number of responders for each cohort) by the scheduled assessment timepoint that the response was first observed. Additionally, descriptive summary statistics (ie, minimum, maximum, median, Q1 and Q3) will also be presented. Time to response will also be summarised based upon the site investigator tumour data.

Time to response will also be summarised using the irRECIST 1.1 data obtained from ICR.

12.2.5 Progression free survival

Kaplan-Meier plots of PFS will be presented for each cohort. Summaries of the number and percentage of patients experiencing a PFS event, and the type of event (RECIST 1.1 or death) will be provided along with median PFS for each cohort. The proportion of patients APF6 and APF12 will be summarised (using the Kaplan-Meier curve) and presented for each cohort.

Summaries and Kaplan-Meier plots of PFS for each cohort will also be provided using the irRECIST 1.1 data obtained from ICR.

Furthermore, summaries and Kaplan-Meier plots of PFS (using the programmatically derived PFS based on ICR assessments) may also be presented by cohort for the PD-L1 negative patients in Cohort 1, and additionally, for all patients in a combined population of Cohorts 1 and 2.

12.2.6 Overall survival

Kaplan-Meier plots of OS will be presented for each cohort. Summaries of the number and percentage of patients who have died, are still in survival follow-up, are lost to follow-up and have withdrawn consent will be provided along with median OS for each cohort.

The proportion of patients alive at 6 and 12 months will be summarised (using the Kaplan-Meier curve) and presented for each cohort.

Furthermore, OS may also be summarised by cohort for the PD-L1 negative patients in Cohort 1, and additionally, for all patients in a combined population of Cohorts 1 and 2.

12.2.7 Safety data

Safety and tolerability data will be presented for each cohort using the safety population.

AEs (both in terms of MedDRA preferred terms and CTCAE grade) will be listed individually by patient. The number of patients experiencing each AE will be summarised by CTCAE grade for each cohort.

Other safety data will be assessed in terms of physical examination, clinical chemistry, haematology, vital signs and ECGs. Exposure to MEDI4736 will be summarised. Time on study and MEDI4736 dose delays will also be summarised. At the end of the study, appropriate summaries of all safety data will be produced, as defined in the SAP.

12.2.8 PK data

MEDI4736 concentration data will be listed for each patient and each dosing day, and a summary provided for all evaluable patients.

12.2.9 Immunogenicity analysis

Immunogenicity results will be listed by patient and a summary will be provided of the number and percentage of patients who develop detectable anti-MEDI4736 antibodies. The immunogenicity titre will be listed for samples confirmed positive for the presence of anti-MEDI4736 antibodies.

12.2.10 PK/pharmacodynamic relationships

If the data are suitable, the relationship between MEDI4736 PK exposure and efficacy/safety parameters may be investigated graphically or using an appropriate data modelling approach.

12.2.11 Biomarker data

Summaries and analyses for exploratory biomarkers will be reported outside the CSR in a separate report.

12.2.12 Interim analysis

An interim analysis of Cohort 2 will be performed after all patients have received one dose of study therapy. This analysis will include preliminary evaluation of efficacy and safety results on PD-L1 positive treated patients.

Additional interim analyses may also be conducted after a minimum follow-up of 8 and 12 weeks respectively from the last treated patient in Cohort 2. The primary efficacy analysis population for these analyses will be the treated PD-L1 positive patients with measurable disease at baseline per the ICR who have had an opportunity of being followed up for at least 24 weeks by the interim analysis DCO. A supportive efficacy analysis will be based on the treated PD-L1 positive patients with measurable disease at baseline per the ICR who have had an opportunity of being followed up for at least 16 weeks by the interim analysis DCO. The interim analysis will be performed on ORR, DoR, DCR, TTR, PFS, OS and key safety endpoints.

The purpose of these interim analyses will be for early evaluation of efficacy and safety data for potential interactions with regulatory agencies on future development of MEDI4736. There are no plans to stop the study early based on these interim results and no formal statistical adjustments are planned. The primary efficacy analysis will take place approximately 24 weeks after the last patient is enrolled into the cohort.

Separate interim analyses of the combined population of Cohorts 2 and 3 for $\geq 90\%$ PD-L1 positive patients will be performed after approximately 100 patients in this group have had the opportunity to be followed up for at least 8 weeks. At this time, similar analyses will be performed for the non-squamous $\geq 90\%$ PD-L1 positive patients. These analyses will follow a similar approach to that mentioned above for the Cohort 2 interim analyses performed at the 8 and 12 week minimum follow-up periods.

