11.1.7 Progression free survival

Progression free survival (per RECIST 1.1 as assessed by the ICR) will be defined as the time from the date of first dose until the date of objective disease progression or death (by any cause in the absence of progression) regardless of whether the patient withdraws from therapy or receives another anti-cancer therapy prior to progression. Patients who have not progressed or died at the time of analysis will be censored at the time of the latest date of assessment from their last evaluable RECIST 1.1 assessment. However, if the patient progresses or dies after 2 or more missed visits, the patient will be censored at the time of the latest evaluable RECIST 1.1 assessment. If the patient has no evaluable visits or does not have baseline data they will be censored at Day 1 unless they die within 2 visits of baseline.

The PFS time will always be derived based on scan/assessment dates not visit dates.

RECIST 1.1 assessments/scans contributing towards a particular visit may be performed on different dates. The following rules will be applied:

- Date of progression will be determined based on the earliest of the dates of the component that triggered the progression on the first set of scans that indicates progression.
- When censoring a patient for PFS the patient will be censored at the latest of the dates contributing to a particular overall visit assessment.

In the absence of clinically significant deterioration the investigational site is advised to continue the patient on MEDI4736 until progression has been confirmed.

For exploratory purposes, PFS will also be obtained using the irRECIST 1.1 data obtained from ICR. Objective disease progressions will require confirmation under this approach.

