12.1.1 Full analysis set (FAS)

Intention-to-treat: The statistical analysis of the efficacy of MEDI4736 will include all treated patients who have a baseline tumour assessment and have measurable disease at baseline according to the investigator site assessment. Patients who were enrolled but did not subsequently go on to receive investigational product are not included in the FAS population. This analysis set will be subsetted for the primary statistical analysis of the efficacy of MEDI4736 for ORR; namely all treated patients who have a baseline tumour assessment and have measurable disease at baseline according to the ICR.

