Subsequent to the availability of the PD-L1 diagnostic to determine PD-L1 positive patients at the $\geq 25\%$ cut-point, only those patients with a tumour that is determined to be PD-L1 positive from a central test are permitted into the study. In the case of those patients who were already recruited prior to the availability of this PD-L1 diagnostic, a PD-L1 status can be determined retrospectively based on the patient's pre-treatment tumour sample. The diagnostic itself has been based upon data external to this study (eg, from Study 1108) and the retrospective PD-L1 testing in this study has been completed only after the diagnostic, including the selected 25% threshold, was made available by [redacted]. Results generated to date have not retrospectively influenced this 25% cut-point selection. Similarly, the decision to use the $\geq 90\%$ cut-point in Cohort 3 was based upon data external to this study (Study 1108). For Cohorts 1 and 2, the analysis of PD-L1 positive patients will include all patients regardless of whether their PD-L1 status was determined prospectively or retrospectively.

For each cohort, the data cut-off for the analysis of ORR will take place approximately 24 weeks after the last patient is enrolled into each cohort.

The data cut-off for the final analysis of OS (secondary endpoint) will take place approximately 12 months after the last patient is enrolled into each cohort.

Descriptive statistics will be used for all variables, as appropriate. Continuous variables will be summarised by the number of observations, mean, standard deviation, median, minimum, and maximum. Categorical variables will be summarised by frequency counts and percentages for each category. Unless otherwise stated, percentages will be calculated out of the population total and for each cohort.

Baseline will be the last assessment of the variable under consideration prior to the intake of the first dose of investigational product, except for efficacy variables. For efficacy variables, baseline is defined as the last visit prior to enrolment.

Efficacy data will be summarised and analysed on the FAS (ie, it will follow the Intention to treat principle) and the FAS subset for measurable disease per ICR for the ORR primary analysis.

The primary analysis population of Cohorts 1 and 3 for the primary endpoint, ORR, and for the secondary endpoints is as follows:

- Cohort 1: PD-L1 positive patients ($\geq 25\%$ of tumour cells with membrane staining)

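### The 8- and 12-week interims place PFS and OS in a set built for response rate (ICR-measurable, at least 24 weeks' potential follow-up), at odds with the FAS that the protocol assigns to these endpoints

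*Protocol*

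**What the plan says.** Section 12.2.12, repeated in the synopsis under the methods specific to Cohort 2, allows additional interims once the last treated Cohort 2 patient has 8 and 12 weeks' follow-up. On the population it says: "The primary efficacy analysis population for these analyses will be the treated PD-L1 positive patients with measurable disease at baseline per the ICR", further limited to those "who have had an opportunity of being followed up for at least 24 weeks by the interim analysis DCO". The supportive analysis keeps the ICR condition and relaxes only the time, to patients "who have had an opportunity of being followed up for at least 16 weeks by the interim analysis DCO". The endpoint list follows directly: "The interim analysis will be performed on ORR, DoR, DCR, TTR, PFS, OS and key safety endpoints". No separate set is given for PFS or OS. The combined Cohort 2 and 3 interim in patients with at least 90% staining is to follow a similar approach.

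Elsewhere the assignment differs. Table 9 places PFS and OS in the FAS. Section 12.1.1 says that the efficacy analysis "will include all treated patients who have a baseline tumour assessment and have measurable disease at baseline according to the investigator site assessment", and takes the ICR-measurable subset of it only for the primary ORR analysis. Section 12.2 repeats that split.

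**The concern.** A response proportion needs a denominator in which response could be measured and had time to occur, so an ICR-measurable set with a follow-up floor suits ORR. It does not suit PFS or OS. Under Section 11.1.8, OS runs from first dose to death and needs no tumour measurement. Under Section 11.1.7, PFS runs from first dose to progression or death; progression may come from non-target or new lesions, and the overall-response table in Appendix F has rows for patients without target lesions. Both sections already censor patients whose follow-up is short.

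Followed as written, Section 12.2.12 leaves out of interim PFS and OS everyone first treated in the last 16 weeks of accrual (8-week interim) or the last 12 weeks (12-week interim), plus those without ICR-measurable disease. The final analysis brings them back. Interim and final curves then describe different populations, and the interim curves are less precise than the available data allow. The stated purpose of these interims is discussion with regulatory agencies, where both matter.

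**Working it through.** **Inputs from the protocol (Section 12.3).** 94 investigator-measurable patients per cohort; about 15% not measurable per ICR; 80 evaluable. Minimum follow-up m = 8 or 12 weeks (Section 12.2.12). Median survival of approximately 6 months in refractory disease (Sections 1.1.1 and 1.3), taken as 26 weeks.

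**Assumptions.** The protocol gives no accrual length. Accrual is taken as uniform over A = 26, 39, 52 or 78 weeks, and OS as exponential.

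**The plan's own figures.** 94 × (1 − 0.15) = 79.9, which matches 80. Exact 95% intervals are 16.0% to 35.9% for 20/80 and 29.2% to 51.6% for 32/80, as stated.

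**Loss from ICR-measurability alone.** 94 − 80 = 14 patients, or 14/94 = 14.9%. The standard error grows by about √(94/80) = 1.08.

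**Adding the follow-up floor.** At the cut-off, potential follow-up is uniform on m to m + A. The share with at least f weeks is 1 − (f − m)/A, so the set size is 80 × [1 − (f − m)/A].

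| Accrual (weeks) | 24-week set, m = 8 | 24-week set, m = 12 | 16-week set, m = 8 | 16-week set, m = 12 |
|---|---|---|---|---|
| 26 | 30.8 | 43.1 | 55.4 | 67.7 |
| 39 | 47.2 | 55.4 | 63.6 | 71.8 |
| 52 | 55.4 | 61.5 | 67.7 | 73.8 |
| 78 | 63.6 | 67.7 | 71.8 | 75.9 |

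The primary set therefore leaves out about 26 to 63 of 94 patients across the whole table.

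**Precision of 24-week OS at the 8-week interim.** Kaplan-Meier estimates from 3,000 simulated cohorts per setting, comparing all 94 with the 24-week set, where ICR-measurability is random with probability 80/94. Ratios were taken before rounding.

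| Accrual (weeks) | SE, all 94 | SE, 24-week set | Ratio |
|---|---|---|---|
| 26 | 0.063 | 0.091 | 1.45 |
| 39 | 0.057 | 0.073 | 1.30 |
| 52 | 0.055 | 0.065 | 1.20 |
| 78 | 0.054 | 0.062 | 1.15 |

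Mean estimates were 0.525 to 0.529 in both sets, against a true value of 2^(−24/26) = 0.527. The loss in this model is in precision.

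**Possible shift from case mix.** If survival at 6 months in the 14 patients without ICR-measurable disease differed from the other 80 by 5, 10 or 20 points (assumed), leaving them out would move the estimate by 14/94 of that: 0.7, 1.5 or 3.0 points.

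**The case against.** The strongest reply is that the endpoint list only says what is reported. It includes safety, which belongs to the safety set, so it cannot bind every item to the restricted set; the FAS would then remain the default for PFS and OS. That reading is possible. However, the only efficacy populations named for these interims, primary and supportive, are both ICR-measurable with a follow-up floor, and the list follows without any exception for PFS or OS. The conflict with Table 9 remains and needs a sentence to settle it.

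Several limits on the weight of the point stand. The Cohort 2 interims at 8 and 12 weeks are optional, with no stopping and no adjustment. The first Cohort 2 interim uses PD-L1 positive treated patients with neither restriction. The supportive set recovers part of the loss: about 55 to 74 of 94 at 26 to 52 weeks' accrual.

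Three stronger readings are tempting and are not supported:

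- **That the final OS and PFS analyses also lose patients materially.** Inclusion criterion 7 requires measurable disease of every patient, exceptions are barred, and a baseline scan is scheduled. The FAS should be close to all treated patients; only those treated in error or without a baseline assessment fall out.
- **That Section 11.1.7 contradicts the FAS.** Its rule that a patient who "does not have baseline data they will be censored at Day 1 unless they die within 2 visits of baseline" belongs to ICR-assessed PFS, whereas FAS membership rests on the site's assessment. A FAS patient may lack a usable baseline at central review, and the same sentence covers patients with no evaluable visits. The clause is at most partly redundant.
- **That the interim estimates are biased.** The 24-week floor selects on entry date, not outcome. ICR-measurability could change case mix, but nothing in the protocol shows a survival difference.

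**Conclusion.** The point holds for the interim wording. Section 12.2.12 and the synopsis apply ICR-measurability and a 24- or 16-week floor to interim PFS and OS, while Sections 12.1.1 and 12.2 and Table 9 put these endpoints in the FAS. About 14 of 94 patients are lost to the ICR condition on the protocol's own 15%. With the 24-week floor, about 31 to 62 of 94 remain for assumed uniform accrual of 26 to 52 weeks, and up to about 68 at 78 weeks. The standard error of 24-week OS at the 8-week interim is inflated by a factor of about 1.15 (78 weeks' accrual) to 1.45 (26 weeks), under exponential OS with a 26-week median. The sizes depend on accrual length, which the protocol does not give. The consequence is avoidable imprecision and an interim population that differs from the final one. Error rates, stopping and the final analysis are unaffected. The change is worth making because it costs nothing; the trial's conclusions do not depend on it.

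**What to change.** In Section 12.2.12 and the matching synopsis text:

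- State that the ICR-measurable sets with at least 24 weeks (primary) and 16 weeks (supportive) of potential follow-up apply to the response endpoints: ORR, DCR, TTR, and DoR among the responders in those sets.
- State that interim PFS and OS are analysed in all PD-L1 positive patients of the FAS, the same set as at the final analysis, with censoring as in Sections 11.1.7 and 11.1.8.
- Say that the same split applies to the combined Cohort 2 and 3 interim, using the FAS patients with at least 90% staining.

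The FAS definition, Table 9 and Section 11.1.7 need no change. The cost is a few sentences in two places, with no extra patients, visits or data.

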12.3 Determination of sample size

The sample size for this study was selected to be consistent with the research hypothesis as described in Section 1.2.

Objective response rate is the primary endpoint. This study will comprise 3 cohorts:

- Cohort 1: *EGFR/ALK* positive, PD-L1 positive patients (defined as $\geq 25\%$ of tumour cells with membrane staining)
- Cohort 2: *EGFR/ALK* wild type, PD-L1 positive patients (defined as $\geq 25\%$ of tumour cells with membrane staining)

- Cohort 3: *EGFR/ALK* wild type, PD-L1 positive patients with $\geq 90\%$ of tumour cells with membrane staining

It is planned to have approximately 94 patients with tumours prospectively determined to be PD-L1 positive (as defined above) in each of the Cohorts 1 and 2. As the diagnostic to determine PD-L1 status was not available when the study first started there will be a number of patients in Cohorts 1 and 2 with tumours determined to be PD-L1 negative, PD-L1 positive or possibly unknown (based retrospectively on the patient's pre-treatment tumour sample).

The study is designed to estimate the response rates for at least 80 evaluable patients in each cohort. This assumes that approximately 15% of patients in each cohort will not be eligible for the primary analysis due to being assessed as having measurable disease by the investigator but not ICR (Douillard et al 2013).

The total number treated in each of the first 2 cohorts is dependent upon the number of patients already treated when the PD-L1 assay cut-off became available and the status of those patients. For example, if 10 patients have been treated in Cohort 1 and 3 of those patients are PD-L1 positive and 7 are PD-L1 negative then a further 91 PD-L1 positive patients will be treated to obtain 94 PD-L1 positive patients in that cohort. In this example the total number of patients in the cohort would be 101 (ie, 94 positive and 7 negative).

In the case of each cohort of 94 patients who have measurable disease per the site investigator and assuming that 80 patients have measurable disease per the ICR, the 2-sided exact 95% CI for the ORR will be (16.0%, 35.9%) provided the observed ORR is 25.0% (based upon 20 patients responding out of 80 patients). Similarly, if the observed ORR is 40.0% (based upon 32 patients responding out of 80 patients) then a 2-sided 95% CI for the ORR will be (29.2%, 51.6%).

